## Script

Child and parent arrive on Children's Perioperative Unit (CPU) and settle into room.

**T1** occurs as standard of care and routine assessment parameters. (See corresponding mYPAS-SF form).

Study is introduced to the family and questions answered. If family is interested in participating, consents and assents are signed. Once signed, child/family is considered enrolled into the study.

Study investigator asks parent to complete demographic information form, and asks both child and parent about the child's age and experience with an iPad.

*Hi! My name is \_\_\_\_\_. I am a (Nurse, NP, Nursing student) and I work with children. I am interested in seeing if an iPad is something that is helpful to use if children have to wait for appointments or procedures, kind of like what you are doing today waiting for your procedure. Would you like to help out by answering some questions while your Mom(my)/Dad(dy) fill out papers for me?*

*How old are you? (child). How old is your child? (parent)*

*Have you ever played with an iPad? What kind of things have you played on the iPad?*

*(child) Has your child ever played with an iPad? What kind of things has your child played on the iPad? (parent).*

Study investigator records these answers on study forms.

*I have an iPad that you can play with while you are waiting here at the hospital. It has 3 games you can choose from. You can play it the whole time you are waiting and then play it again when you wake up. Which game would you like to play?*

Investigator indicates which game is chosen on demographic sheet.

T2 occurs just prior to introduction of anesthesia. (See corresponding mYPAS-SF form). This may mean that the iPad travels to the OR. If the iPad does travel, it will be retrieved and returned to the Peds CPU to await the child's return post-surgical procedure.

T3 occurs when child awakens from the sedated procedure in the CPU. (See corresponding mYPAS-SF form).

*Hi! \_\_\_\_\_ (insert name of child) your procedure is all done and I have the iPad here if you would like to continue your game. Would you like to play with it?*

Child continues to play with the iPad until cleared to be discharged at which time the iPad is collected and the Chick Fil A gift card is given.

*Thanks for helping me out today and playing with the iPad. I hope that you had a good time. While you are getting ready to go home, I will take the iPad so that I can recharge it, and since you were so helpful, I want you to have this Chick Fil A gift card.*

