## Project: REACH UP!

### Statistical Analysis Plan

This study was designed as a small pilot study with its purpose to discern the means and SD between the groups to determine the appropriate effect size for future work. The pilot study size was set at 12 children for the control group and 12 children for the intervention group. Recruitment occurred at the day of the child's scheduled procedure and participants were randomized via a computer algorithm varying by block sizes of 2 and 4 to blind the investigator at the time of consent.

Analysis included comparison of time points as related to scores on the mYPAS-SF, with group 1 time points (anxiety scores) compared to group 2 time points (anxiety scores). The comparison was desired to see if there was an effect on the scores with the introduction of the iPad (intervention). Means and SD of each time point were calculated and a t test was used to analyze the two groups and then correlate within and between the groups. To discern effect size, the Cohen's d calculation was used.

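### Does the plan need a further mYPAS-SF rating because the last one, T3, comes before the post-procedure iPad play?

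*Combined protocol and SAP*

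**What the plan says.** The Script lists three mYPAS-SF assessments. T1 "occurs as standard of care and routine assessment parameters" and is placed before consent, so before any iPad is offered. T2 is taken shortly before anaesthesia begins, after the waiting-period play. For the third, "T3 occurs when child awakens from the sedated procedure in the CPU".

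The child is told at the outset: "You can play it the whole time you are waiting and then play it again when you wake up". After T3 the investigator is scripted to say "your procedure is all done and I have the iPad here if you would like to continue your game". Play then runs to discharge: "Child continues to play with the iPad until cleared to be discharged at which time the iPad is collected". The closing words, "While you are getting ready to go home, I will take the iPad so that I can recharge it", mention no rating.

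The Statistical Analysis Plan describes a pilot of 12 control and 12 intervention children "with its purpose to discern the means and SD between the groups to determine the appropriate effect size for future work". It compares mYPAS-SF scores between groups by time point, in order to "see if there was an effect on the scores with the introduction of the iPad (intervention)". It names no other outcome.

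**The concern.** The intervention as scripted has two play periods. The first has a score before it (T1) and after it (T2). The second has a score before it (T3) and, as listed, none after it. The product of this pilot is a set of means, SDs and effect sizes for later work, so it matters what each one measures.

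T3 is the only score after the procedure, and the intervention includes play after the procedure. A reader could therefore take the T3 difference, or its Cohen's d, as the effect of that later play. It is not: it reflects the earlier play and any expectation of more to come. If a later study of post-procedure play were sized on the T3 value, its sample size would rest on the wrong quantity. The SAP does not warn against this.

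**Working it through.** The plan has no stated figure to reproduce. The 12 per group was set as a pilot size, without alpha, power, SD or target effect. The main check is the order of events.

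**1. Timeline, from the Script.** T1, consent, iPad offered, play while waiting, T2, procedure, T3 on waking, iPad offered again, play until discharge, iPad collected.

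**2. Count.** Scheduled ratings: 3 time points x 24 children = 72. Ratings listed after post-procedure play starts: 0. The Script points to a mYPAS-SF form for T3 that is not in the supplied text, and waking is not timed to the minute, so T3 might overlap the first moments of play. Even so, it would not be an end-of-play score.

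**3. Count against the stated aims.** The Script's introduction to the child describes the interest as whether an iPad helps children who have to wait. The SAP's question concerns the iPad being introduced. That happens between T1 and T2, and both are scored. Neither document sets an aim for the period between waking and discharge. Every comparison the SAP names can be made with T1, T2 and T3 as they stand.

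**4. What a fourth rating would give.** Up to 24 more ratings: 72 + 24 = 96, and 24/72 = 33% more. Children in the intervention group receive both play periods, so a between-group Cohen's d at that point would combine them and would not isolate the later one. A rating tied to iPad collection falls at each child's own discharge time, which gives controls no natural matching time. A fixed interval since waking would avoid that, but needs a contact with controls that the Script does not describe.

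**5. Whether the risk to later sample sizes can be quantified.** Take as assumptions two-sided alpha 0.05, 80% power and a true post-play d of 0.5, which needs 64 per group. A T3 d of 0.25 would suggest 253 per group. A T3 d of 0.75 would suggest 29 per group, with about 46% power for d = 0.5. All three d values are invented, and nothing in the documents shows which way T3 would differ from a post-play score. The approximate 95% half-width for d with 12 per group is 1.96 x sqrt(2/12 + d²/48):

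- d = 0: 1.96 x sqrt(0.1667) = 0.80
- d = 0.5: 1.96 x sqrt(0.1667 + 0.0052) = 0.81
- d = 0.8: 1.96 x sqrt(0.1667 + 0.0133) = 0.83

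An observed d of 0.5 would have an interval of 0.5 ± 0.81, or -0.31 to 1.31, which contains both 0.25 and 0.75. This pilot could not tell those values apart with or without a fourth rating, so the illustration does not measure what the extra rating would gain.

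**The case for a change.** The best argument for a change is that post-procedure play is no incidental courtesy. It is promised before the procedure and scripted until discharge, and the SAP does not confine the intervention to the waiting period. A pilot meant to supply effect sizes should, on this view, either score that period or say that it does not, and a sentence in the SAP costs almost nothing.

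Part of this stands. The sequence is as described, no later score is listed, and T3 should not be read as a result of post-procedure play. But the argument shows only that an additional outcome could have been collected. It does not show that a planned comparison fails. The SAP nowhere proposes to use the T3 effect size for a study of post-procedure play, and misreading it that way means overlooking the Script's own definition of T3. The SAP is also written in the past tense, so another rating may no longer be possible. What then remains is a point of wording that an analyst can put in the report without amending the plan.

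**Conclusion.** No change to the plan is needed. On the supplied text, 0 of 72 scheduled ratings follow post-procedure play, so the pilot gives no effect size for that period. No stated aim depends on one. T1 and T2 bracket the waiting-period play, T3 is a valid between-group score on waking, and following the plan as written produces no wrong result. A later rating is an optional outcome with its own drawbacks (up to 24 more ratings, a timed contact for controls, and a Cohen's d that mixes both periods). Leaving it out is a fair trade-off in a pilot of this size.

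A careful report would say that the T3 difference and its Cohen's d reflect pre-procedure exposure and any expectation of further play, and do not evaluate play after the procedure. A study aimed at that later period could add a rating in both groups at a matched time since waking.

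This conclusion assumes that T3 is scored in the order in which the Script lists it, and that no document outside the supplied text sets an aim for the post-procedure period. If such an aim existed, the missing score would matter more.

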## Project: REACH UP!

### Statistical Analysis Plan

This study was designed as a small pilot study with its purpose to discern the means and SD between the groups to determine the appropriate effect size for future work. The pilot study size was set at 12 children for the control group and 12 children for the intervention group. Recruitment occurred at the day of the child's scheduled procedure and participants were randomized via a computer algorithm varying by block sizes of 2 and 4 to blind the investigator at the time of consent.

Analysis included comparison of time points as related to scores on the mYPAS-SF, with group 1 time points (anxiety scores) compared to group 2 time points (anxiety scores). The comparison was desired to see if there was an effect on the scores with the introduction of the iPad (intervention). Means and SD of each time point were calculated and a t test was used to analyze the two groups and then correlate within and between the groups. To discern effect size, the Cohen's d calculation was used.

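### The SAP reads as if the Cohen's d seen in 12 v 12 children will be the design effect size of later work; the pilot's SD, paired with a worthwhile difference, is the sounder input

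*Combined protocol and SAP*

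**What the plan says.** The Statistical Analysis Plan describes a small pilot with "its purpose to discern the means and SD between the groups to determine the appropriate effect size for future work". On size: "The pilot study size was set at 12 children for the control group and 12 children for the intervention group". On outcome: "Analysis included comparison of time points as related to scores on the mYPAS-SF". On method: "Means and SD of each time point were calculated and a t test was used to analyze the two groups". It then says: "To discern effect size, the Cohen's d calculation was used".

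The Script section has the mYPAS-SF scored at three points: T1 on the unit before enrolment, T2 immediately before anesthesia, and T3 on waking. The SAP does not say which of these supplies the d of interest. Neither section gives a mYPAS-SF difference that would be worth detecting, an expected SD, a confidence interval for d, or an alpha or power for later work.

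**The concern.** Taken together, the purpose sentence and the Cohen's d sentence point to the observed standardised difference as the number handed to the next study. That raises two problems.

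- **It answers a different question.** The effect size that should size a trial is the smallest difference that matters to children and clinicians. An observed d is the difference that happened to occur in 24 children, divided by an SD.
- **It is noisy where the SD is not.** With 22 degrees of freedom the pilot estimates the SD tolerably well and the mean difference poorly. Folding both into d discards the advantage of the SD.

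A chance-large d would make the next trial too small to find a worthwhile effect, and a chance-small d would make it needlessly large. A d at or below zero gives no usable size. An interval around d would show the imprecision, but would not help if the point estimate were still the value carried forward.

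**Working it through.** **Inputs from the documents:** 12 per group, 1:1, a t test on mYPAS-SF scores, and Cohen's d. The 12 per group has no alpha, power, SD or difference behind it, so there is no sample size calculation to reproduce.

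**Assumptions, not in the documents:** normal scores, equal variances, no dropout, and a next trial with 80% power at two-sided 5%. True d is taken as 0.5, with 0.3 and 0.8 as the range.

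**1. Precision of d.** With t = d x sqrt(12/2) on 22 df, invert the noncentral t and divide the noncentrality limits by sqrt(6). For d = 0.5, t = 0.5 x 2.449 = 1.22.

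| Observed d | 95% limits |
|---|---|
| 0.5 | -0.32 to 1.31 |
| 0.8 | -0.04 to 1.63 |
| 1.0 | 0.14 to 1.84 |

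**2. Precision of the pooled SD.** The multipliers are sqrt(22/36.78) = 0.77 and sqrt(22/10.98) = 1.42. Sample size goes with SD squared, so for a fixed difference it varies by a factor of 0.60 to 2.00.

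**3. Size needed at d = 0.5.** The normal formula gives 2 x (1.960 + 0.842)^2 / 0.5^2 = 62.8, so 63 per arm. The noncentral t gives 64, which is used below.

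**4. Chance of d at or below zero when the true d is 0.5.** Phi(-0.5 / sqrt(2/12)) = Phi(-1.22) = 0.11.

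**5. Next trial sized on the observed d.** Pilots of 12 v 12 were simulated. Each positive d was converted to the n per arm giving 80% power at that d (capped just under 3,000), and the power of that n was then taken at the true d.

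| True d | Mean true power | Next trials under 50% power |
|---|---|---|
| 0.3 | 57% | 49% to 50% |
| 0.5 | 67% | 34% |
| 0.8 | 74% | 23% |

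At true d 0.5 the middle 80% of sizes run from 14 to about 650 per arm. Separate runs put the upper end between 633 and 659, because it lies in a long tail.

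**6. Next trial sized on the pilot SD and a fixed difference.** With the difference fixed at 0.5 true SDs, the middle 80% of sizes run from 42 to 89 per arm. Mean power at that difference is 78%, and about 2% of trials fall under 50%. Fixing it at 0.3 or 0.8 SD instead leaves mean power at that difference at 77% to 78% and the share under 50% at about 2%.

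**7. One case.** Suppose 0.5 SD is worth detecting and the pilot shows d = 0.9. Sizing on 0.9 gives 21 per arm, which has 35% power for 0.5 SD.

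**The case against.** **The rule is inferred.** The SAP does not mention a sample size for later work, nor say that the point estimate of d will be used unadjusted. Calling the effect size appropriate leaves room for judgement, and the means and SDs that a better calculation needs are already computed. This stands, so the point is about the natural reading and not about an explicit instruction. An effect size fixed by a pilot for later work does, however, have no other evident use here.

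**The comparison can flatter the alternative.** Setting the fixed difference equal to the truth gives that method the answer. If the true d is 0.5 but 0.6 SD is chosen, mean power at the truth is 63%, with 14% of trials under 50%. If 0.8 SD is chosen, the figures are 42% and 79%, worse than the observed-d rule. This also stands. The claim that survives is narrower: power at the difference chosen as worthwhile stays near 78%. It does not protect a trial whose true effect is smaller than that.

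**The consequences lie outside this study.** Nothing in the treatment or measurement of these children changes, and a later designer could take the reported SD and ignore d. This is fair, and it is why the point is a cheap improvement and not a flaw in the conduct of the pilot.

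**The SAP is in the past tense.** If the study is complete, rewriting its aim afterwards would be wrong. How the results are reported and used can still follow the advice.

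**A pilot need not be powered.** Agreed. The 12 per group is not criticised.

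**Conclusion.** The point holds as a caution about design logic. On its natural reading, the SAP offers later work a number that is very imprecise at 12 v 12 and that does not say which difference is worth detecting, while the more useful quantity, the SD, is already being calculated. If the observed d were used as it stands with a true d of 0.5, about one pilot in nine would give no usable size, and about a third of the remaining next trials would have under 50% power. All of these figures rest on the assumed normality, alpha, power and true d.

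Three stronger readings are not supported:

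- A reader might infer that the SAP lays down an explicit sample size rule. It does not.
- A reader might infer that supplying this number is the pilot's sole aim. The SAP also wants to see whether the iPad affected scores.
- A reader might infer that a small or negative d would end the programme. The documents contain no go/no-go criterion.

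**What to change.** Reword the purpose sentence along these lines: *The pilot estimates the pooled between-child SD of the mYPAS-SF at a named time point (for example T2). Future work will be sized on this SD and on a mYPAS-SF difference, in points, judged worthwhile on clinical grounds independently of the pilot result. The observed Cohen's d is descriptive and is not the design effect size.*

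The time point has to be named because scores are taken at T1, T2 and T3. Say also whether the SD is of the score or of a change in score. Report the raw mean difference and pooled SD in points, and d with its 95% interval. Because the SD is itself uncertain, later work could use an upper confidence limit for it.

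If the study is already complete, leave the stated aim alone and apply this to the report and to any later sample size calculation.

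Cost: a few sentences and a short clinical discussion, with no added children, visits or measurements. The downside is that the worthwhile difference must be justified clinically and cannot be read off the pilot.

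### The pilot's effect size comes from an unadjusted t test, although T1, scored on the same scale before consent, could serve as a baseline covariate

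*Combined protocol and SAP*

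**What the plan says.** The SAP describes the study in these terms: "small pilot study with its purpose to discern the means and SD between the groups to determine the appropriate effect size for future work". On size it states: "The pilot study size was set at 12 children for the control group and 12 children for the intervention group". On method it states: "Means and SD of each time point were calculated and a t test was used to analyze the two groups", followed by an instruction to "correlate within and between the groups" and a Cohen's d calculation. It names no covariate, ANCOVA or change score, and it does not say what SD Cohen's d is divided by.

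The Script section sets the order of events. T1 "occurs as standard of care and routine assessment parameters", on an mYPAS-SF form, as the family settles in. Only then is the study explained and consent taken: "Once signed, child/family is considered enrolled into the study". T2 is scored on the same instrument just before anesthesia, and so is the last score: "T3 occurs when child awakens from the sedated procedure in the CPU".

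**The concern.** T1 is measured on the outcome scale before the family has agreed to take part. The Script shows no randomisation step, so it is an inference that T1 precedes randomisation. The SAP supports it, because it is participants who are randomised, with varying block sizes meant to keep the investigator blind at the time of consent. On that reading the iPad cannot affect T1, which makes it a proper baseline covariate.

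Leaving it out does not bias the comparison. The unadjusted T2 or T3 difference is unbiased under randomisation, and its confidence interval already allows for chance imbalance at T1. But if children who are anxious at T1 tend to be anxious later, the t test carries variance that a covariate could remove. The precision of the effect size matters here because that estimate is the pilot's main product.

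Two further gaps follow from the wording:

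- The SAP does not say which t tests are run or what "correlate within and between the groups" means. If the within-group part means comparing change from T1, that is not a substitute for adjustment; it can be less precise than the plain t test.
- The within-child T1-T2 and T1-T3 correlations are planning inputs for any later baseline-adjusted trial. The SAP does not clearly call for them.

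**Working it through.** The SAP gives no alpha, power, SD or target difference behind 12 per arm, so there is no sample-size calculation to reproduce. The check compares the precision of three analyses at that size.

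**Inputs**
- From the SAP: n = 12 per arm, N = 24.
- Assumed: outcome SD = 1, so results are in SD units; two-sided 95% intervals; r = 0, 0.3, 0.5 and 0.7.
- Assumed for the formulas: normally distributed T1, a common slope in both arms and complete data on all 24 children. The change-score line also assumes equal SDs at T1 and at the outcome.

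**Unadjusted t test**
- SE = sqrt(2/12) = 0.408.
- Half-width = t(22) × SE = 2.074 × 0.408 = 0.847.

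**ANCOVA on group and T1**
- Variance relative to the t test = (1 − r²) × [1 + 1/(N − 4)] = (1 − r²) × 21/20. The factor 21/20 is the average cost of estimating the slope.
- Half-width = t(21) × 0.408 × sqrt(variance ratio), with t(21) = 2.080.

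**Change from T1**
- Variance relative to the t test = 2(1 − r).

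| r (assumed) | ANCOVA variance ratio | ANCOVA 95% half-width (SD) | Change-score variance ratio |
|---|---|---|---|
| 0 | 1.050 | 0.870 | 2.0 |
| 0.3 | 0.956 | 0.830 | 1.4 |
| 0.5 | 0.788 | 0.753 | 1.0 |
| 0.7 | 0.536 | 0.621 | 0.6 |

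**Break-even points**
- ANCOVA against t test, on variance: r = sqrt(1 − 20/21) = 0.218. With 20 children it would be sqrt(1/17) = 0.243.
- ANCOVA against t test, on interval width, counting the lost degree of freedom: r = 0.230.
- Change score against t test: 2(1 − r) = 1, so r = 0.5.
- Change score against ANCOVA: 2(1 − r) = 1.05(1 − r²), so 1 + r = 2/1.05 and r is about 0.90.

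**Simulation check.** With 200,000 simulated trials per r, the ANCOVA variance ratios were 1.049, 0.956, 0.786 and 0.538 at the four values of r, and 1.001 at r = 0.218. In a separate run of 100,000 trials per r, the ANCOVA interval was narrower than the t-test interval in 20%, 53%, 85% and 99% of trials.

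**What the gain is worth.** Dividing 12 by the variance ratio gives the unadjusted size of equal precision: 12/0.788 = 15.2 per arm at r = 0.5 and 12/0.536 = 22.4 at r = 0.7. For a later, larger trial the required size scales roughly by 1 − r²: 25% fewer children at r = 0.5 and 51% fewer at r = 0.7.

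**How well the pilot can estimate r.** For r pooled within arm, Fisher's z has SE = 1/sqrt(20) = 0.224. An observed 0.5 has z = 0.549, limits 0.549 ± 1.96 × 0.224 = 0.111 to 0.988, and so a 95% CI for r of about 0.11 to 0.76.

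**Standardiser for d.** Dividing by the residual SD from the ANCOVA would inflate d by 1/sqrt(1 − r²), which is 1.15 at r = 0.5 and 1.40 at r = 0.7. The raw pooled SD avoids this.

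**The case against.** The strongest reply is that nothing is invalid. A two-sample t test after randomisation is sound, and raw means, SDs and d deliver what the SAP says the pilot is for. The benefit of adjusting rests wholly on an r the documents do not give. At r = 0 it does slight harm. At r = 0.3 it is worth about one child (24/0.956 = 25.1), and the interval is narrower in only 53% of trials. T3 is scored on waking from sedation, so its link to T1 may be weaker than at T2. Even at r = 0.5, an illustrative observed d of 0.5 has an interval of −0.25 to 1.25 instead of −0.35 to 1.35; both include zero, and neither fixes a future sample size. The loose wording could also hide a change-score analysis or already include the within-child correlations. Finally, the SAP is in the past tense, so the analysis may be finished.

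Most of this stands as a limit on how strongly the point can be put. The issue is efficiency, not validity; the gain is uncertain, more so at T3; and 12 per arm remains the main constraint. It does not remove the point. The possible loss is about 3% in interval width, against a gain of 11% at r = 0.5 (0.753/0.847 = 0.89) and 27% at r = 0.7 (0.621/0.847 = 0.73). A hidden change-score analysis would not be equivalent, and the present wording is too vague to reproduce whatever was meant. The SAP also plans no confidence interval, a gap that matters whatever r is.

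**Conclusion.** The concern holds as a worthwhile, low-cost improvement. The SAP names no baseline covariate, although T1 is already collected on the outcome scale before consent. A T1-adjusted difference has lower variance than the t test if r exceeds about 0.22 (0.23 on interval width). Zero gain lies at that threshold; a material gain starts at about r = 0.5.

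The text and the arithmetic are firm. The size of the gain is not, because r is unknown and may differ between T2 and T3. The figures also rest on T1 preceding randomisation and on the modelling assumptions listed with the calculation. The unadjusted result remains valid, and adjustment does not make a 24-child pilot precise.

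**What to change.** - Make the between-group estimate at T2, and separately at T3, an ANCOVA on randomised group and T1 score. Report the adjusted difference with its 95% CI.
- Define Cohen's d as the adjusted difference divided by the raw pooled SD.
- Keep the raw means, SDs and t test beside it, and state which time points the t tests compare.
- Describe T1 by group without testing it.
- Replace "correlate within and between the groups" with the within-child T1-T2 and T1-T3 correlations, pooled within arm, with CIs.
- State that T1 is scored before randomisation, if that is so.
- If the analysis has already been run, label the ANCOVA as added afterwards.

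The cost is SAP wording and one model term, with no new data, visits or children. It uses one degree of freedom, and if T1 is unrelated to the outcome the half-width grows from 0.85 to 0.87 SD.

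### The SAP plans a between-group correlation that has no pairs of children to correlate, and its t test of the two groups leaves out each child's T1 score

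*Combined protocol and SAP*

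**What the plan says.** The design is a randomized pilot: "The pilot study size was set at 12 children for the control group and 12 children for the intervention group", and "participants were randomized via a computer algorithm varying by block sizes of 2 and 4". No matching of children across arms is described.

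Each child has an mYPAS-SF score at three times, set out in the Script section. T1 "occurs as standard of care and routine assessment parameters", before the study is introduced and consent is signed. "T2 occurs just prior to introduction of anesthesia", and T3 is on awakening.

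The Statistical Analysis Plan describes the main analysis as "group 1 time points (anxiety scores) compared to group 2 time points (anxiety scores"), and gives its aim in the next sentence: "The comparison was desired to see if there was an effect on the scores with the introduction of the iPad (intervention"). Means and SDs are calculated at each time point. The only sentence that names a test reads "a t test was used to analyze the two groups and then correlate within and between the groups". Cohen's d follows. The plan names no variables, coefficient or purpose for the correlation, and no adjustment for T1.

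**The concern.** Two things are wrong with the one sentence that names a test.

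First, a correlation needs two values from the same unit, or from units linked by design. A child in the control arm and a child in the iPad arm are not linked. Anyone who tried to correlate the arms' scores would have to line up two lists of children in some order, and the order would decide the answer.

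Second, the comparison that does address the iPad is a plain t test of scores. Some children arrive more anxious than others, and with 12 per arm the arms can differ at T1 by chance. The T1 score is available for every enrolled child at no extra burden, yet it enters only as one of the time points and is not linked to that child's T2 or T3 score.

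At stake are an output that would mean nothing if run as worded, and precision lost in the estimate that the pilot exists to pass on to the next trial.

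**Working it through.** **Inputs from the documents.** 12 children per arm, 24 in all; individual randomization without matching; scores at T1, T2 and T3; T1 before enrolment. The figure of 12 was set, not derived: there is no alpha, power, SD or target effect, so there is no calculation to reproduce.

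**Assumed, not in the documents.** Two-sided 95% intervals, roughly normal scores with equal SD in both arms, and a T1-T2 correlation r of 0.3, 0.5 or 0.7.

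**1. Correlating scores across arms.** Hold both lists of n scores fixed and pair them in random order. The coefficient then has mean 0 and variance 1/(n − 1):

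- SD = 1/√11 = 0.30
- central 95% range ≈ ±1.96 × 0.30 = ±0.59

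In one simulated pair of independent 12-child samples, re-ordering alone moved r from −0.93 to +0.71, with a central 95% range of −0.64 to +0.50. The coefficient carries no information about the iPad.

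**2. Correlating score with group membership.** This is the point-biserial correlation, and it is well defined. With 24 children, t = r√(22/(1 − r²)), which is exactly the pooled two-sample t statistic. In a simulated example both routes gave t = 2.175 and p = 0.0407. Under this reading the extra step repeats the t test and adds nothing.

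**3. What T1 could contribute.** Chance alone gives the between-arm difference in mean T1 an SD of √(2/12) = 0.41 score SDs. An unadjusted T2 comparison carries r times that imbalance; at r = 0.5 this is 0.5 × 0.41 = 0.20 SD. ANCOVA removes it.

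The ratio of 95% CI widths, adjusted to unadjusted, has three factors:

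- √(1 − r²), the residual SD after adjustment
- √(1 + 1/20) = 1.0247, the average price of chance T1 imbalance (1/(24 − 4) for a normal covariate)
- t(21)/t(22) = 2.0796/2.0739 = 1.0028, the lost degree of freedom

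The last two multiply to 1.0275.

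| r | √(1 − r²) | × 1.0275 | CI narrower by |
|---|---|---|---|
| 0.3 | 0.954 | 0.980 | 2% |
| 0.5 | 0.866 | 0.890 | 11% |
| 0.7 | 0.714 | 0.734 | 27% |

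In score-SD units the unadjusted half-width is 2.0739 × √(2/12) = 0.847. Adjusted, it becomes 0.830, 0.753 and 0.621.

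**4. Where adjustment would not pay.** The ratio reaches 1 when √(1 − r²) = 1/1.0275, that is r = √(1 − 1/1.0275²) ≈ 0.23. Below that the interval is slightly wider, by at most 2.75% at r = 0.

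**The case against.** The strongest reply is that the sentence is loose more than wrong. It may mean a t test followed by a separate correlation, or it may use correlate to mean compare. The text cannot settle which, so it is not established that anyone planned to line up unrelated children. That is fair, but no reading rescues the between-group half: score with score has no pairs, score with group repeats the t test, and compare has already been said.

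A reader might go further and infer three things that the documents do not support.

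- *That the SAP judges the iPad by within-arm change.* It does not: the stated aim follows the comparison of group 1 with group 2. Within-arm tests would indeed mislead. With no iPad effect and a shared change of 0.5 to 0.8 SD, a paired test in the iPad arm is significant in 27% to 91% of simulated trials (r from 0.3 to 0.7, two-sided 5% level), against 4.8% to 5.3% for between-arm tests. Those figures measure an error that the plan does not say it makes. They are a reason to label within-arm output descriptive, and no more.
- *That repeated scores from one child are tested unpaired.* The plan says only that a t test was used for the two groups. It is silent on pairing.
- *That no between-group correlation can exist.* That is too absolute, as the point-biserial case shows.

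The within-group half of the phrase is legitimate and lacks only detail. The correlation of T1 with later scores is a useful pilot output, though the next trial needs it only if it adjusts for baseline or analyses change; a plain comparison of T2 means can be sized from means and SDs.

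It can also be said that ANCOVA is a preference, and that a plan written in the past tense may describe work already done. The unadjusted t test is valid under randomization, so the gain is in precision, not validity. The timing point stands and is met by labelling.

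**Conclusion.** The point holds in limited form. The between-group correlation is either undefined, with an SD of 0.30 from list order alone at 12 per arm, or a restatement of the t test. It should not be in the plan. The between-arm comparison is the right basis for the iPad question but leaves out a baseline score that is already collected. Using it would narrow the 95% CI by about 2%, 11% or 27% at assumed T1-T2 correlations of 0.3, 0.5 or 0.7. The benefit disappears below about 0.23, and the documents give no value for this correlation.

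The consequence is modest. The pilot's purpose is to estimate means, SDs and an effect size, and none of these depends on the correlation clause. Nothing in the documents supports the stronger charge that efficacy is to be read from within-arm results.

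**What to change.** In the Statistical Analysis Plan, replace the sentence that names the t test with four statements:

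1. There is no correlation of scores between the groups.
2. The iPad effect is the between-arm difference in mYPAS-SF at T2 and at T3, each adjusted for the child's T1 score by ANCOVA, with 95% CI.
3. Within-arm change is reported as the mean and SD of each child's paired differences, described only and not used as evidence for the iPad.
4. The pooled within-arm correlation of T1 with T2 and of T1 with T3 is reported with 95% CI, for use if the next trial adjusts for baseline.

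The planned means, SDs and Cohen's d stay. The cost is one degree of freedom per model, some SAP wording and a few lines of code. No new children, visits or measurements are needed. If the data have already been analysed, report the planned t test as well and label the adjusted analysis as added later.
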